5.3.2.2 Non-Hematologic Toxicity

Toxicity	Action
AST or ALT elevation Grade 1 (> ULN - 3.0 x ULN) Grade 2 (> 3.0 - 5.0 x ULN)	Maintain current dose level
AST or ALT elevation Grade 3 (> 5.0 - 20.0 ULN)	Interrupt everolimus/placebo administration until resolution to ≤ grade 1 (or ≤ grade 2 if baseline values were within the range of grade 2). If resolution occurs ≤ 7 days, everolimus/placebo should be re-started at the dose level prior to interruption.
	If resolution takes > 7 days, or if event recurs within 28 days, hold everolimus/placebo until recovery to ≤ grade 1 or baseline grade / value and reintroduce everolimus/placebo at one dose level lower, if available.
AST or ALT elevation Grade 4 (> 20 x ULN)	Interrupt everolimus/placebo administration until resolution to ≤ grade 1 (or ≤ grade 2 if baseline values were within the range of grade 2). If resolution occurs ≤ 7 days, everolimus/placebo should be re-started at one dose level lower. If resolution takes > 7 days, discontinue everolimus/placebo.
Intolerable grade 3 AE, except hyperglycemia or	Interrupt everolimus/placebo administration until resolution to ≤ grade 1 or baseline grade / value.
hypertriglyceridemia or hypercholesterolemia	If resolution occurs within ≤ 7 days, everolimus/placebo should be re-started at the dose level prior to interruption.
	If resolution takes > 7 days, or if event recurs within 28 days, hold everolimus/placebo until recovery to ≤ grade 1 or baseline grade / value and reintroduce everolimus/placebo at one dose level lower, if available.
	Patients will be withdrawn from the study if they fail to recover to ≤ grade 1 or baseline grade / value within 28 days.
Any other grade 4 non- hematologic	Hold everolimus/placebo until recovery to grade ≤ 1 or baseline value
, and the second	Reintroduce everolimus/placebo at one dose level lower, if available.
Grade 3 or 4 clinical liver failure (asterixis or encephalopathy/coma)	Discontinue everolimus/placebo
Recurrence of intolerable grade 2 mucositis or grade 3 event after dose reduction	Reduce dose to the next lower dose level, if available.
Recurrence of grade 4 non- hematologic toxicity after dose reduction	Discontinue protocol treatment.
Any non-hematologic toxicity requiring Everolimus/Placebo interruption for > 28 days	Discontinue protocol treatment.

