5.3.2 Everolimus/Placebo Dose Modifications

 For individual subjects, dose modifications will be based on hematologic or non-hematologic toxicity, laboratory test results,

- and clinical assessment on the day of treatment and during the previous cycle.
- If dose delays are required, weekly evaluation with laboratory tests and clinical assessments, if applicable, should be performed until recovery to the specified grade or until the subject is discontinued from the study.
- If toxicities have not resolved within ≤ 4 weeks (28 days), patient must discontinue protocol treatment.
- The study chair or study chair liaison should be contacted for dose delays and modifications for all other toxicities not listed in this section.
- One dose reduction is permitted before everolimus/placebo will be discontinued. Patients who require further dose reductions beyond the -1 dose level must be discontinued from study treatment.

Everolimus/Placebo Dose Level Table			
Dose Level	Dose in mg		
0	10 mg daily		
-1	5 mg daily		

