5.3.2.2.1 Mucositis¹

Category	Grade	Everolimus/placebo dose modification	
Mucositis oral	Grades 1	No dose modification.	
	Grades 2-4	Hold until ≤ grade 1 then reduce by one dose level.	

Please refer to Section 5.4.2 for mucositis and stomatitis supportive care information.

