5.3.2.2.2 Stomatitis¹

Adverse Drug Reaction	Severity	Everolimus/Placebo Dose Adjustment and Management Recommendations
Stomatitis	Grade 1	No dose adjustment required.
	Grade 2	Hold until grade ≤1. Re-initiate everolimus/placebo at same dose. If stomatitis recurs at grade 2, hold until ≤ grade 1 then reduce by one dose level.
	Grade 3	Hold until ≤ grade 1 then reduce by one dose level.
	Grade 4	Discontinue protocol therapy and treat with appropriate medical therapy.

1. Please refer to Section 5.4.2 for mucositis and stomatitis supportive care information.

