5.3.2.2.4 Metabolic Events: Hyperlipidemia and Hyperglycemia

Hyperglycemia has been reported in clinical trials. Monitoring of fasting serum glucose is recommended prior to the start of everolimus/placebo and periodically thereafter. Optimal glycemic control should be achieved before starting a patient on everolimus/placebo.

Category	Grade	Everolimus/Placebo Dose Adjustment and Management Recommendations
Metabolic events (e.g. hyperglycemia, dyslipidemia)	Grade 1	No dose adjustment required. Initiate appropriate medical therapy and monitor.
	Grade 2	No dose adjustment required. Manage with appropriate medical therapy and monitor.
	Grade 3	Hold until ≤ grade 1 then reduce by one dose level. Manage with appropriate medical therapy and monitor.
	Grade 4	Discontinue protocol therapy and treat with appropriate medical therapy.

5.3.2.2.5 **Pulmonary Toxicity**

Category	Grade	Everolimus/placebo dose modification
Vital	Grades 1	Obtain CT scan with lung windows. Continue previous dose of treatment.
Capacity Abnormal	Grade 2	Obtain CT scan with lung windows. Obtain pulmonary function testing including spirometry, DLCO, and room air O2 saturation at rest. Hold protocol treatment until toxicity improves to ≤ grade 1, then resume with one dose level reduction of treatment. Steroids may be used at the discretion of the treating physician for relief of symptoms associated with pulmonary toxicity.
	Grade 3	Obtain CT scan with lung windows and pulmonary function testing including spirometry, DLCO, room air O2 saturation at rest, and bronchoscopy. Hold protocol treatment until recovery to ≤ grade 1, then resume treatment with one dose level reduction. Steroids may be used at the discretion of the treating physician for relief of symptoms associated with pulmonary toxicity.
	Grade 4	Obtain CT scan with lung windows and pulmonary function testing including spirometry, DLCO, room air O2 saturation at rest, and bronchoscopy. Discontinue protocol treatment. Steroids may be used at the discretion of the treating physician for relief of symptoms associated with pulmonary toxicity.

Non-Infectious Pneumonitis 5.3.2.2.6

Non-infectious pneumonitis is a class effect of rapamycin derivatives. Cases of noninfectious pneumonitis (including interstitial lung disease) have also been described in patients taking Everolimus. Some of these have been severe and on rare occasions, a fatal outcome was observed.

E2212

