A diagnosis of non-infectious pneumonitis should be considered in patients presenting with non-specific respiratory signs and symptoms such as hypoxia, pleural effusion, cough or dyspnea, and in whom infectious, neoplastic and other non-medicinal causes have been excluded by means of appropriate investigations. Patients should

be advised to report promptly any new or worsening respiratory symptoms.

Consultation with a pulmonologist is recommended for any case of pneumonitis that develops during the study.

Worst grade pneumonitis	Suggested investigations	Management of pneumonitis	Everolimus/placebo dose adjustment
Grade 1	CT scans with lung windows.	No specific therapy is required	No dose adjustment required. Initiate appropriate monitoring.
Grade 2	CT scan with lung windows. Consider pulmonary function testing includes: spirometry, DLCO, and room air O₂ saturation at rest. Consider a bronchoscopy with biopsy and/or BAL. Monitoring at each visit until return to ≤ grade 1. Return to initial monitoring frequency if no recurrence.	Symptomatic only. Consider corticosteroids and/or other supportive therapy if symptoms are troublesome.	Rule out infection and consider interruption of Everolimus/placebo until symptoms improve to Grade ≤ 1. Re-initiate Everolimus/placebo at one dose level lower. Discontinue Everolimus/placebo if failure to recover within ≤ 28 days.
Grade 3	CT scan with lung windows and pulmonary function testing includes: spirometry, DLCO, and room air O2 saturation at rest. Monitoring at each visit until return to ≤ grade 1. Return to initial monitoring frequency if no recurrence. Bronchoscopy with biopsy and/or BAL is recommended.	Consider corticosteroids if infective origin is ruled out. Taper as medically indicated.	Rule out infection and interrupt Everolimus/placebo until symptoms improve to Grade ≤ 1. Consider re-initiating Everolimus/placebo at one dose level lower. Discontinue protocol therapy if failure to recover within ≤ 28 days.
Grade 4	CT scan with lung windows and required pulmonary function testing, if possible, includes: spirometry, DLCO, and room air O2 saturation at rest. Monitoring at each visit until return to ≤ grade 1. Return to initial monitoring frequency if no recurrence. Bronchoscopy with biopsy and/or BAL is recommended if possible.	Consider corticosteroids if infective origin is ruled out. Taper as medically indicated.	Rule out infection and discontinue protocol ttreatment.

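### The general non-hematologic rows and the event-specific tables give different dosing instructions for some grade 3 events, leave grade 4 ambiguous, and no sentence says which governs

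*Combined protocol and SAP*

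**What the plan says.** All references are to the combined protocol and SAP.

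- **Dose levels (5.3.2).** Level 0 is 10 mg daily and level -1 is 5 mg daily. "One dose reduction is permitted before everolimus/placebo will be discontinued", and "Patients who require further dose reductions beyond the -1 dose level must be discontinued from study treatment". Section 5.3.1 makes any reduction permanent.
- **General grade 3 row (5.3.2.2).** The label begins "Intolerable grade 3 AE, except hyperglycemia or" and goes on to name the two lipid events. If the event resolves in time: "If resolution occurs within ≤ 7 days, everolimus/placebo should be re-started at the dose level prior to interruption". Slower resolution, or recurrence within 28 days, leads to one level lower.
- **General grade 4 row (5.3.2.2).** For *any other* grade 4 non-hematologic event, drug is held until recovery and then reintroduced one level lower.
- **Oral mucositis (5.3.2.2.1), grades 2 to 4.** "Hold until ≤ grade 1 then reduce by one dose level".
- **Stomatitis (5.3.2.2.2).** Grade 3 carries the same instruction as mucositis. Grade 4 reads "Discontinue protocol therapy and treat with appropriate medical therapy".
- **Metabolic events (5.3.2.2.4), grade 4.** The wording is the same as for grade 4 stomatitis.
- **Vital capacity (5.3.2.2.5).** Grade 3 resumes with a one-level reduction; grade 4 discontinues.
- **Pneumonitis (5.3.2.2.6).** Grade 3: "Consider re-initiating Everolimus/placebo at one dose level lower". Grade 4 discontinues.
- **Precedence.** None is stated. The nearest text, in 5.3.2, refers sites to the study chair or liaison only for toxicities that the section does not list.

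**The concern.** A site faced with one of these events can find two applicable instructions that lead to different doses. The events are not remote: Section 8.1.13 lists stomatitis, pneumonitis, diabetes mellitus and hypercholesterolemia among the known effects of everolimus. Because a reduction is permanent, choosing one text over the other fixes the dose for the rest of the course. At grade 4 the choice may be between renewed exposure and a permanent stop, which is a patient-safety matter. Objective 2.2.2 is to evaluate toxicity, and delivered dose could differ between sites for reasons unrelated to the patient. The route to the study chair does not help, because these toxicities are listed.

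**Working it through.** The plan states no figure on this point, so the check sets the texts side by side for a **first event in a patient at 10 mg**.

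| Event | General row of 5.3.2.2 | Event-specific table | Agree? |
|---|---|---|---|
| Grade 3 oral mucositis, resolved ≤ 7 days | 10 mg | 5 mg | No |
| Grade 3 stomatitis, resolved ≤ 7 days | 10 mg | 5 mg | No |
| Grade 3 vital capacity, resolved ≤ 7 days | 10 mg | 5 mg | No |
| Grade 3 pneumonitis, resolved ≤ 7 days | 10 mg | consider 5 mg | No, but discretionary |
| Grade 3 hyperglycemia or the two named lipid events | excepted | 5 mg | No conflict |
| Grade 3 oral or vital capacity event, resolved in 8 to 28 days | 5 mg | 5 mg | Yes |
| Grade 4 stomatitis, metabolic, vital capacity or pneumonitis | 5 mg, if the row applies | stop | Depends on *any other* |
| Grade 4 oral mucositis | 5 mg | 5 mg | Yes |

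The grade 3 rows that differ do so only if the event is judged intolerable (a term the section does not define) and does not recur within 28 days.

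**Patient already at 5 mg.** A new intolerable grade 3 event that resolves in 7 days or less restarts at 5 mg under the general row. Under a table that requires a reduction, no lower level exists, so 5.3.2 means a stop. If the event is instead a recurrence after reduction, a separate row of 5.3.2.2 applies and also calls for the next lower level, so this split concerns new events.

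**Size for one patient.** Inputs are 28-day cycles, 12 cycles at most (5.1.1) and the dose levels in 5.3.2.

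- Planned dose: 12 × 28 × 10 mg = 3,360 mg.
- Days left after cycle 1: 11 × 28 = 308.
- Grade 3 at level 0, 10 mg against 5 mg: 308 × (10 − 5) = 1,540 mg.
- Share of plan: 1,540 / 3,360 = 45.8%.
- Grade 4 at level 0, 5 mg against none, if the general row applies: 308 × (5 − 0) = 1,540 mg, the same share.

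These figures take the event at the end of cycle 1, all 12 cycles completed under the higher-dose reading, no days lost to the hold, and no later modification. The gap shrinks with a later event: at the end of cycle 6 it is 6 × 28 × 5 = 840 mg, or 840 / 3,360 = 25%.

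**The case against.** The best defence is that a specific table governs a general row. Sections 5.3.2.2.1 to 5.3.2.2.6 are numbered under 5.3.2.2. Within the general table itself, a liver-failure row sits below the *any other* grade 4 row and requires discontinuation, so *other* there seems to mean events without their own instruction. Carried to the sub-sections, that reading removes the grade 4 conflict. The label of the grade 4 row is also broken in the text copy, so an exception could have been lost. This much stands: **grade 4 is an ambiguity, not a proven contradiction.** It remains open because the protocol does not state that reading.

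The defence is weaker at grade 3. That row has no word *other*. It lists exceptions, and the excepted events have their own table; if a specific table prevailed automatically, the exceptions would be unnecessary. Another row of the general table names recurrent mucositis, so that table is evidently meant to reach an event with its own sub-section.

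Several limits also stand:

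- The grade 3 conflict needs an intolerable event, resolution in 7 days or less and no recurrence within 28 days.
- Pneumonitis at grade 3 is a matter of discretion, not a fixed reduction.
- Section 5.4.2 treats stomatitis, oral mucositis and mouth ulcers together, so the oral tables should not be counted as wholly separate events.
- Re-exposure at grade 4 is partly contained: it follows recovery to grade 1 or baseline, a recurrence of grade 4 after reduction means discontinuation, and unacceptable toxicity ends therapy under 5.5.3.

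A reader might infer that the conflict distorts the disease-free survival comparison. The documents do not support that. They give no frequency of qualifying events, the trial is blinded, the primary analysis takes all randomized eligible patients, and Section 9 says that formal comparison of toxicity rates is not a goal.

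**Conclusion.** The point holds in limited form. For an intolerable grade 3 event that resolves in 7 days or less without recurring within 28 days, the general row contradicts the oral mucositis, stomatitis and vital capacity tables, and differs from the discretionary pneumonitis instruction. The readings are 10 mg or 5 mg for a first event at full dose, and 5 mg or stop for a new event at the reduced dose. At grade 4, whether the stomatitis, metabolic, vital capacity and pneumonitis tables conflict with the general row depends on a phrase that the protocol leaves undefined.

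It would go too far to say that every grade 3 or grade 4 event with its own table is contradicted: the three named metabolic events are excepted at grade 3, and oral mucositis agrees at grade 4. The 46% is an upper bound for one patient with an event at the end of cycle 1, on the assumptions shown. It is not an average or an effect on Arm A, and no effect on disease-free survival can be stated. The point should be corrected because the instructions concern expected toxicities and patient safety.

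**What to change.** Reconcile the general rows of 5.3.2.2 with 5.3.2.2.1, 5.3.2.2.2, 5.3.2.2.4, 5.3.2.2.5 and 5.3.2.2.6, so that each event and grade has one instruction. State which text governs when a general row and an event-specific table both apply, and say what *any other* covers in the grade 4 row. Check that row's label against the source document at the same time. Which instruction is kept is a clinical decision for the study chair.

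The cost is a few edited rows and one sentence in the next amendment, with a memo to sites. Data collection, sample size and the analysis are unaffected.

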5.3.2.2.1 Mucositis¹

Category	Grade	Everolimus/placebo dose modification	
Mucositis oral	Grades 1	No dose modification.	
	Grades 2-4	Hold until ≤ grade 1 then reduce by one dose level.	

Please refer to Section 5.4.2 for mucositis and stomatitis supportive care information.

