5.1.2 Treatment/ARM B

Placebo PO daily

Repeat cycles every 28 days for a maximum duration of 12 cycles.

Rev. 5/14 Adverse Event Reporting Requirements

5.2.1 **Purpose**

Adverse event (AE) data collection and reporting, which are required as part of every clinical trial, are done to ensure the safety of the patients enrolled, as well as those who will enroll in future studies using similar agents.

- **Routine reporting**: Adverse events are reported in a routine manner at scheduled times during a trial using Medidata Rave.
- Expedited reporting: In addition to routine reporting, certain adverse events must be reported in an expedited manner for timelier monitoring of patient safety and care. The following sections provide information and instructions regarding expedited adverse event reporting.

5.2.2 **Terminology**

- Adverse Event (AE): Any untoward medical occurrence
 associated with the use of a drug in humans, whether or not
 considered drug related. Therefore, an AE can be ANY
 unfavorable and unintended sign (including an abnormal
 laboratory finding), symptom, or disease temporally associated
 with the use of a medicinal product, whether or not considered
 related to the medicinal product.
- Attribution: An assessment of the relationship between the adverse event and the protocol treatment, using the following categories.

ATTRIBUTION	DESCRIPTION
Unrelated	The AE is clearly NOT related to treatment.
Unlikely	The AE is doubtfully related to treatment.
Possible	The AE may be related to treatment.
Probable	The AE is likely related to treatment.
Definite	The AE is clearly related to treatment.

- CTCAE: The NCI Common Terminology Criteria for Adverse Events provides a descriptive terminology that is to be utilized for AE reporting. A grade (severity) is provided for each AE term.
- Hospitalization (or prolongation of hospitalization): For AE reporting purposes, a hospitalization is defined as an inpatient hospital stay equal to or greater than 24 hours.
- Life Threatening Adverse Event: Any AE that places the subject at immediate risk of death from the AE as it occurred.
- **Serious Adverse Event (SAE):** Any adverse event occurring at any dose that results in **ANY** of the following outcomes:
 - Death
 - A life-threatening adverse event
 - Inpatient hospitalization or prolongation of existing hospitalization (for ≥ 24 hours).

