5.3.1 General

If dose reduction is required, reduction is permanent. Missed doses may be taken up to 6 hours after normally scheduled time. If more than 6 hours have elapsed, patient should be instructed to skip the dose for that day. The next day, they should take everolimus/placebo at the usual time. Patients should not take 2 doses to make up for the one that they missed.

If multiple toxicities are seen, the dose administered in a subsequent cycle should be based on the most severe toxicity experienced in the current cycle.

AEs determined to be unrelated to study treatment will not require dose reduction.

If everolimus/placebo is held for > 4 weeks (28 days), patient must discontinue protocol treatment.

All toxicities should be graded according to the Common Terminology Criteria for Adverse Events (version 4.0).

All appropriate treatment areas should have access to a copy of the CTCAE version 4.0. A copy of the CTCAE version 4.0 can be downloaded from the CTEP website (http://ctep.cancer.gov).

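### The oral mucositis and stomatitis tables give different dosing for a first grade 2 event and, less directly, for grade 4, and no rule says which table governs

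*Combined protocol and SAP*

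**What the plan says.** Two adjacent tables cover oral inflammation. Section 5.3.2.2.1 (oral mucositis) makes no change at grade 1. At grades 2, 3 and 4 alike the instruction is "Hold until ≤ grade 1 then reduce by one dose level". Section 5.3.2.2.2 (stomatitis) makes no change at grade 1. At a first grade 2 event it says "Hold until grade ≤1. Re-initiate everolimus/placebo at same dose", with a one-level reduction only if grade 2 returns. At grade 3 it holds and reduces. At grade 4 it says "Discontinue protocol therapy and treat with appropriate medical therapy".

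Both tables refer to Section 5.4.2 for supportive care. That section treats stomatitis, oral mucositis and mouth ulcers together and describes grades 2 and 3 once for all three, by pain and by whether the patient can keep up oral intake. It also asks sites to record mouth ulcers under that name when that is what they see.

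Two general rules raise the stakes. Section 5.3.1 says "If dose reduction is required, reduction is permanent". Section 5.3.2 allows a single step, from 10 mg to 5 mg, and adds "Patients who require further dose reductions beyond the -1 dose level must be discontinued from study treatment".

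On terminology, Section 5.2.2 says that CTCAE "provides a descriptive terminology that is to be utilized for AE reporting", and Section 5.3.1 says "All toxicities should be graded according to the Common Terminology Criteria for Adverse Events (version 4.0)".

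**The concern.** Two sites could see the same grade 2 picture, follow the protocol exactly, and dose the patient differently because one wrote mucositis and the other stomatitis. With only one permanent reduction available, that choice of word can use up the reduction or, for a patient already at 5 mg, end study treatment. The toxicity is anticipated: Section 8.1.13.1 lists stomatitis as a side effect, and Section 8.1.14 warns patients about all three oral terms.

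The tables also differ in opposite directions. Mucositis is the stricter at grade 2 and stomatitis the stricter at grade 4. An informal habit of following the more cautious table would therefore switch tables by grade, and the protocol states no such habit.

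**Working it through.** There is no planned figure to reproduce. The check applies each table to one event of each grade and compares the resulting dose.

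Inputs: the dose ladder of 10 mg, 5 mg, then off (Section 5.3.2); the mucositis steps (5.3.2.2.1: none at grade 1, one level down at grades 2 to 4); and the stomatitis steps (5.3.2.2.2: none at grade 1, none at first grade 2, one level down at grade 3, off at grade 4). Rule: resulting dose = current level minus the steps given, and any step below 5 mg means off. The 5 mg start assumes that the earlier reduction was for a different toxicity, so the recurrence rows of Section 5.3.2.2 do not apply.

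| Event | From 10 mg: mucositis / stomatitis | From 5 mg: mucositis / stomatitis |
|---|---|---|
| Grade 1 | 10 mg / 10 mg | 5 mg / 5 mg |
| First grade 2 | 5 mg / 10 mg | off / 5 mg |
| Grade 3 | 5 mg / 5 mg | off / off |
| Grade 4 | 5 mg / off | off / off |

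From 10 mg, two of the four grades differ. From 5 mg, one of four differs.

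Can one event fall under both tables? At grades 2 and 3, Section 5.4.2 gives one clinical description for all three terms, so the same picture carries the same grade whichever term is used. It has no grade 4 step, so the grade 4 overlap rests on the shared management of the terms and not on a shared grade description.

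Does any other rule settle which table applies?

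- Section 5.3.1 doses on the most severe of several toxicities. It does not choose between two tables for one event of one grade.
- Section 5.3.2 refers toxicities that the section does not list to the study chair or liaison. Both of these are listed.
- The mucositis row in Section 5.3.2.2 deals with recurrence after a reduction, not with a first event.
- The general grade 4 row in Section 5.3.2.2 holds and reduces, as the mucositis table does, but it does not say that it overrides the stomatitis table.
- The classification sentence in Section 5.4.2 separates mouth ulcers from general inflammation. It does not separate mucositis from stomatitis.

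None of them does.

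A related point affects the fix. The general row for an intolerable grade 3 event says "If resolution occurs within ≤ 7 days, everolimus/placebo should be re-started at the dose level prior to interruption". Both oral tables reduce at grade 3 however quickly the event resolves. A merged table therefore has to state its precedence over the general rows.

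**The case against.** The strongest reply is that the tables are keyed to different adverse event terms. Because events are reported in CTCAE terminology and graded by version 4.0, the recorded term might select the table. This stands in part. The documents do not show whether CTCAE separates the two terms, so a reader who infers that sites are free to pick either label goes further than the text allows. What can be said is that the protocol itself gives no criterion for telling them apart.

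A reader might also treat the grade 4 conflict as just as firm as the grade 2 one. It is not: the shared description stops at grade 3, and the mucositis rule at grade 4 agrees with the general grade 4 row.

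A third tempting inference is that mouth ulcers have no dosing rule because neither table names them. Section 5.3.2 refers unlisted toxicities to the study chair, and Section 5.3.2.2 has general rows for intolerable grade 3 and other grade 4 events, so they are partly covered.

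Finally, the safeguards are real. Both tables hold or stop drug at grades 2 to 4, any restart needs recovery to grade 1 or lower, and a hold of more than 28 days ends treatment (Sections 5.3.1 and 5.3.2.2). Unacceptable toxicity also ends it (Section 5.5.3). These limit the harm but do not remove the inconsistency.

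**Conclusion.** The point stands as a contradictory dosing rule that should be fixed. The main conflict is the first grade 2 event: 5 mg against 10 mg from full dose, or off drug against 5 mg once the reduction has been used. The grade 4 difference, 5 mg against discontinuation from full dose, is secondary because its overlap is less directly supported.

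The conclusion assumes that one clinical picture can be recorded under either term, which Section 5.4.2 supports at grades 2 and 3. The documents give no incidence for any of the three terms, so no number of affected patients is offered.

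A reader might infer that inconsistent dosing weakens the primary comparison. The documents do not support that: nothing in them links these tables to type I error, power or disease-free survival, and no such effect is claimed.

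**What to change.** Replace Sections 5.3.2.2.1 and 5.3.2.2.2 with one table for oral mucositis, stomatitis and mouth ulcers:

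- Grade 1: no change.
- First grade 2: hold to grade 1 or lower and restart at the same dose; reduce one level on recurrence.
- Grade 3: hold to grade 1 or lower, then reduce one level.
- Grade 4: discontinue.

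State that this table takes precedence over the general rows of Section 5.3.2.2 for these terms, including the 7-day same-dose restart at grade 3 and the mucositis recurrence row. Amend the classification sentence in Section 5.4.2 so that recording an event as mouth ulcers does not change the dosing rule.

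The cost is one clarification memo or amendment, with no statistical cost. There are two clinical downsides. A first grade 2 event labelled mucositis no longer triggers an automatic reduction, and a grade 4 event labelled mucositis can no longer resume at 5 mg, although the general grade 4 row would allow it. The alternative at grade 2, adopting the mucositis rule, would make every first grade 2 event use up the single permitted reduction.
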